#### 3.3.1.2.3 Continuous endpoints

Percent change in brain volume at the EOS compared to Month 6 will be analyzed using a mixedeffect model with repeated measures (MMRM) approach in the ITT population for estimating the treatment effect with appropriate transformation if necessary (eg, log-transform). Estimates derived from the MMRM approach will be weighted by overall proportion of participants in

each stratum or categorical factor. The model will include percent change from Month 6 values at scheduled visits up to and including the EOS visit as the response variable, and treatment group, age at screening (>40,  $\leq$ 40 years), geographic region (US, non-US), visit, treatment-by-visit interaction, Month 6 brain volume, and Month 6 brain volume-by-visit interaction as covariates; have an unstructured variance-covariance matrix; and be fitted using restricted maximum likelihood estimation. If this model fails to converge, the following variance-covariance structures will be tested in this order:

- Heterogeneous Toeplitz (Toeplitz with non-equal variances)
- Heterogeneous AR(1) (first-order autoregressive with non-equal variances)
- Heterogeneous CS (compound symmetry with non-equal variances)
- Toeplitz (equal variances and a separate correlation for each level of separation between the time points)
- AR(1) (first-order autoregressive, equal variances and exponentially decreasing correlations)
- CS (compound symmetry, equal variances and equal pairwise correlations across fixed time points).

The first (co)variance structure yielding convergence will be used as the primary analysis. Comparisons between treatment arms will be made using least squares means (LSM) contrasts at the EOS with denominator degrees of freedom estimated using the Kenward-Roger approximation (8). When a variance-covariance structure other than unstructured is used, the denominator degrees of freedom will be estimated using the between within method (DDFM=BW in SAS PROC MIXED) (9).

Change from baseline in SDMT number of correct substitutions, CVLT-II total correct and MSQoL-54 physical and mental health composite scores at the EOS will be analyzed using an analogous MMRM approach in the ITT population with the change from baseline values for the respective endpoint at scheduled visits up to and including the EOS visit as response variables, and treatment group, age at screening (>40,  $\leq$ 40 years), geographic region (US, non-US), visit, treatment-by-visit interaction, baseline value for the endpoint being assessed and baseline value-by-visit interaction as covariates.

For each endpoint, difference in LSM, the corresponding 95% CI, and p-value will be estimated from the MMRM model for the comparison of tolebrutinib to placebo using weights for each stratum equal to the overall proportion of participants in each stratum (ie, "Population weight"). Plots of LSM [±standard error (SE)] over time will be provided. Participants who discontinue study intervention before the study end will be asked and encouraged to return for all remaining study visits and the additional off-treatment values measured up through the EOS will be included in the primary analysis. For participants who withdraw from the study before the EOS, values will be missing after study discontinuation and no imputation will be performed.

SDMT, CVLT-II and MSQoL-54 data are assumed a priori to be normally distributed. Given the large sample size, the impact of violation of normality should not be great. In order to assess the impact of deviation from the normality assumption, a sensitivity analysis using rank analysis of

covariance (ANCOVA), with the same covariates as for the MMRM analysis except VISIT and related interaction terms, will be performed to test the significance of the treatment effect.

Given that participants who reach the primary endpoint of 6M-CDP are eligible to switch to OL tolebrutinib, including data after the switch could impact the analysis of secondary endpoints: number of new/enlarging T2 lesions per year, time to onset of sustained 20% increase in the 9-HPT (T25-FW) for at least 3 months, and percent change in brain volume at EOS compared to Month 6. Sensitivity analyses excluding data after initiation of OL therapy will be performed for these endpoints.

No other sensitivity, supplementary, or subgroup analyses will be performed for the secondary endpoints.

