3.1 APPROPRIATENESS OF MEASUREMENTS

Nonrelapsing SPMS is defined as an MS phenotype with progressive disability in the absence of relapse, after an initial variable period of a relapsing-remitting course. Hence, delaying the progression of disability is a clinically relevant outcome and is an aim of any disease-modifying treatment in NRSPMS. Measurement of delay of disability progression is an important clinical endpoint and is endorsed by regulatory guidance (9). The EDSS is widely used to measure neurological disability in clinical trials and routine settings (8). Due to known fluctuation in EDSS scores, CDP confirmed after 3- or 6 months is used as an endpoint in clinical trials of progressive MS (1, 2). Confirmed disability progression lasting for at least 6 months is considered to be more clinically relevant and superior in ruling out EDSS score fluctuations and is therefore chosen as the primary efficacy endpoint in this trial.

Confirmed disability improvement over at least 6 months as measured by the EDSS score will be a secondary endpoint due to its clinical importance. Magnetic resonance imaging measurements will include change in brain volume, which is considered to be a marker of the CNS degenerative process and is therefore recommended in progressive MS (9). Magnetic resonance imaging at Month 6 will serve as the baseline for analyses of MTR and brain atrophy to exclude the potential confounding effect of transient changes in brain volume associated with resolution of inflammation after introduction of treatment (so-called pseudoatrophy) (25). The MRI markers of inflammatory activity in the brain observed in previous clinical trials of progressive MS (1, 2) will also be measured. The number of active T2-hyperintense lesions and change in their volume at the EOS are selected as secondary endpoints, as they reliably reflect accumulating MS lesion load over time.

In addition, MRI measurements will include analysis of brain volume loss over time. Several MS drugs are known for their capacity to slow down brain volume loss, which will be assessed in search of a possible signal.

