9.4.3 Secondary endpoint(s)

For other time-to-event endpoints (time to onset of sustained 20% increase in the 9-HPT, of sustained 20% increase in the T25-FW, of 3-month CDP, and of CDI), similar analysis as for the primary analysis of the primary efficacy endpoint will be performed in the ITT population but without imputation.

Continuous endpoints (percent change in brain volume loss, change in cognitive function, change in physical function, and change in MSQoL-54 at EOS) will be analyzed using a mixed-effect model with repeated measures (MMRM) approach. The model will include change/percent change values for the respective endpoint at each scheduled visit as response variables, and treatment, age at screening (>40, \leq 40 years), geographic region (US, non-US), visit, treatment by-visit interaction, baseline value for the endpoint being assessed and baseline value-by-visit interaction as covariates. Difference in LS means, the corresponding 95% CI, and p-value will be provided for the comparison of SAR442168 versus placebo. For percent change in brain volume loss, log transformation will be applied in the MMRM model. In order to assess the impact of deviation from the normality assumption, a sensitivity analysis using rank ANCOVA with the same covariates as for the MMRM analysis except visit and related interaction terms, will be performed for these continuous endpoints to provide the p-value for the comparison between the treatment groups.

Categorical efficacy endpoints with count data (new and/or enlarging T2 hyperintense over the study period after baseline) will be analyzed using a negative binomial regression model. The model will include the total lesion count across all post-randomization MRI scans during the study period as the response variable, with treatment group, age at screening (>40, \leq 40 years), geographic region (US, non-US), baseline EDSS score, and baseline T2 lesions as covariates. Log-transformed observation duration from screening MRI to last available MRI will be the offset variable. In order to assess the impact of open-label therapy, sensitivity analysis excluding the data after initiation of open-label therapy will be performed for the key secondary endpoints that will be pre-specified in the SAP. Further details including details of missing data handling and subgroup analyses for secondary endpoints will also be detailed in the SAP.

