#### 3.4.2 Main analytical approach

Summary statistics including mean, SD, median, interquartile range (Q1, Q3), minimum, and maximum will be provided for the following continuous data endpoints at scheduled visits over the study period including the EOS. Only non-missing data will be included. For change from baseline, only participants with baseline and post-baseline data will be summarized.

- EDSS score and change from baseline
- Number of Gd-enhancing T1 lesions and change from baseline
- Number of new Gd-enhancing T1 lesions
- Number of new/enlarging T2 lesions per 6-month interval
- T2 lesion volume and change from baseline
- Cumulative number of new T1-hypointense lesions
- T1-hypointense lesion volume and change from baseline.
- Number of phase rim lesions and change from baseline
- Normalized brain volume at screening and percent change in brain volume at post baseline time points
- Number of slowly evolving lesions at EOS compared to screening
- Volume of slowly evolving lesions at EOS compared to screening
- SDMT number of correct substitutions Z-score and change from baseline
- SDMT number of completed items and change from baseline
- CVLT-II standardized scores for total number correct and change from baseline
- CVLT-II standardized scores for total number of intrusions and change from baseline

- CVLT-II standardized scores for total number of repetitions and change from baseline
- MSFC-3 score and change from baseline
- T25-FW raw score and Z-score for leg function/ambulation and change from baseline
- 9-HPT raw score and Z-score for arm/hand function and change from baseline
- MSQoL-54 score and change from baseline for the 2 derived composite scores, 12 subscale scores and 2 single item scores
- EQ-5D-5L health state utility value score and change from baseline
- EQ VAS score and change from baseline

Plots of mean ( $\pm$ SD) and/or mean change ( $\pm$ SD) and/or median over time will also be provided for better visualization.

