#### 3.5 MULTIPLICITY ISSUES

To strongly control the Type 1 error rate for the study, a hierarchical testing procedure will be applied at a 2-sided 5% significance level, ie, each hypothesis will be formally tested only if the preceding one is significant at the 5% level. If statistical significance is achieved for the primary endpoint, a selective set of secondary endpoints will be tested following the hierarchical testing procedure shown below:

- Time to onset of 3-month CDP as assessed by the EDSS score
- Number of new and/or enlarging T2 hyperintense lesions per year
- Time to onset of sustained 20% increase in the 9-HPT for at least 3 months
- Time to onset of sustained 20% increase in the T25-FW for at least 3 months
- Time to onset of CDI confirmed over at least 6 months
- Percent change in brain volume as detected by MRI scans at the EOS compared to Month 6

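### The confirmatory brain-volume MMRM omits baseline MRI predictors the trial already collects; adding them is a small, cheap gain, and a screening-volume version of the model should be run

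*SAP*

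**What the plan says.** SAP 3.5 states that "a hierarchical testing procedure will be applied at a 2-sided 5% significance level". The sixth and last secondary endpoint listed there is "Percent change in brain volume as detected by MRI scans at the EOS compared to Month 6".

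For this endpoint SAP 3.3.1.2.3 specifies: "The model will include percent change from Month 6 values at scheduled visits up to and including the EOS visit as the response variable". Apart from treatment, visit and their interaction, the model contains age in two groups, region, "Month 6 brain volume, and Month 6 brain volume-by-visit interaction as covariates". It has no lesion term.

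The Month 6 reference is deliberate. Protocol 3.1 says that "Magnetic resonance imaging at Month 6 will serve as the baseline for analyses of MTR and brain atrophy", and gives the reason: "to exclude the potential confounding effect of transient changes in brain volume associated with resolution of inflammation after introduction of treatment". For continuous endpoints generally, Protocol 9.4.3 prescribes the "baseline value for the endpoint being assessed and baseline value-by-visit interaction as covariates".

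The baseline MRI data are in hand and partly in use:

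- SAP 3.4.2 summarises "Normalized brain volume at screening and percent change in brain volume at post baseline time points" and also T2 lesion volume with its change from baseline. Its own analysis of T2 volume is on the log scale.
- Baseline Gd status is a covariate in the primary Cox model (SAP 3.2.2), and SAP 3.1 has a rule to impute it when missing.
- Baseline number of T2 lesions is a covariate in the T2 lesion count model (SAP 3.3.1.2.2).

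The one SAP sensitivity analysis that names brain volume excludes data after open-label start, and SAP 3.3.1.2.3 rules out any others for secondary endpoints. The rank ANCOVA in Protocol 9.4.3 carries the MMRM's covariates over, apart from visit and its interactions. So no planned analysis uses a different brain-volume covariate or adds lesion burden.

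**The concern.** Two features of the model invite comment.

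The first is what it leaves out. Lesion burden before treatment is a plausible predictor of later volume loss. The plan already treats Gd status and T2 lesion number as worth adjusting for in other models, but not in the confirmatory model for brain volume. Leaving out a prognostic baseline covariate does not bias a randomized comparison. It does leave avoidable residual variance in a test that has one chance at the 5% level.

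The second is the timing of the volume covariate. Month 6 is about six months after randomization, and the reason given for starting the measurement there accepts that treatment may change volume before then. If it does, the arms differ on the covariate because of treatment, and adjusting for it can move the estimated difference. With no alternative-covariate analysis planned, a reader of the results could not tell whether that had happened.

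**Working it through.** **Figures in the documents.** There is no power, SD, effect size or prognostic R² for brain volume. The only power figure is for the primary endpoint (SAP 4: 288 events, hazard ratio 0.70, 2:1, two-sided 0.05, 80%). By Schoenfeld's formula, √(288 × 1/3 × 2/3) × |ln 0.70| − 1.960 = 8 × 0.3567 − 1.960 = 0.893, and Φ(0.893) = 81.4%, which agrees with the stated 80%. It says nothing about brain volume, so every brain-volume input below is an assumption.

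**Precision from added predictors.** Let R² be the share of the remaining residual variance that baseline T2 volume and Gd status explain beyond the terms already in the model. The SE is multiplied by √(1 − R²). A test with 80% power then has power Φ[(1.960 + 0.842)/√(1 − R²) − 1.960].

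| Incremental R² (assumed) | SE ratio | Power, from 80% |
|---|---|---|
| 0.02 | 0.990 | 80.8% |
| 0.05 | 0.975 | 82.0% |
| 0.10 | 0.949 | 84.0% |
| 0.15 | 0.922 | 86.0% |

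An ANCOVA simulation of the end-of-study contrast, standing in for the MMRM (2000 runs per scenario), points to the low end: SD of the estimate 1% to 4% smaller, and about 1 to 3 points of power. It assumed 900 evaluable at 2:1, SD of percent change 1.2, between-person volume SD 5.5%, SD of change from Month 0 to Month 6 of 0.6%, and measurement error 0.3%.

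**Bias from the Month 6 covariate.** Suppose treatment shifts Month 6 volume by d percent and has no effect on change after Month 6. The adjusted contrast is then off by

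bias = r × (SD of change / SD of Month 6 volume) × d,

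where r is the correlation between Month 6 volume and later percent change. Take SD of change 1.2 and SD of Month 6 volume √(5.5² + 0.6²) = 5.53. For N evaluable at 2:1, SE = 1.2 × √(1 − r²) × √(3/N + 3/(2N)).

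- r = 0.1, d = 0.3, N = 1000: bias = 0.1 × 1.2/5.53 × 0.3 = 0.0065 points; SE 0.0801; ratio 0.08; type I error 5.1%.
- r = 0.2, d = 0.3, N = 1200: bias 0.0130; SE 0.0720; ratio 0.18; type I error 5.4%.
- Extreme corner, r = 0.3, d = 0.5, N = 1200: bias 0.0325; SE 0.0701; ratio 0.46; type I error 7.5%.

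For r up to 0.2, d up to 0.3 and 800 to 1200 evaluable, type I error stays between 5.0% and 5.4%. The simulation agrees: bias about 0 if treatment leaves Month 6 volume alone, 0.09 to 0.21 SE if treatment lowers it by 0.2%, and 0.2 to 0.5 SE if by 0.5%.

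The direction depends on the sign of r, which the documents do not give. If larger volume goes with less later loss and treatment lowers Month 6 volume, the bias favours tolebrutinib.

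**Screening volume instead.** In the same simulation this removed the bias to within simulation error. The SD of the estimate was practically the same under the two covariates (0.0893 for both in one setting; 0.0865 and 0.0874 in another).

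**The case against.** The sponsor can fairly say that the SAP does what the protocol asks. Protocol 3.1 names Month 6 as the atrophy baseline and Protocol 9.4.3 adjusts for the endpoint's baseline, so the covariate is no oversight. That stands. So do these points:

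- Month 6 remains inside the response whichever volume covariate is used, so replacing the covariate does not make the analysis fully anchored at randomization.
- Everyone with a response has a Month 6 volume, so the current covariate drops nobody. Baseline T2 volume or screening volume could be missing, and the SAP has an imputation rule for Gd status only.
- Participants with a gadolinium contraindication may enrol (Protocol 5.2, E 12), so some Gd values may be imputed. The SAP 3.1 rule looks at post-baseline counts and otherwise draws at random. The SAP says few participants are affected.
- Gd status adds little if few participants have enhancing lesions, and the documents do not give that prevalence.
- No later test depends on this one.

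Two stronger readings are tempting, and the documents support neither. A reader might infer that conditioning on Month 6 volume invalidates the test or wastes precision. The calculation shows a small bias under moderate inputs and no precision cost. A reader might also infer a free gain worth 4% to 14% more participants, from correlations of 0.20 to 0.35 with the outcome: 1/(1 − 0.20²) − 1 = 4.2% and 1/(1 − 0.35²) − 1 = 14.0%. Those are assumed marginal correlations. What counts is the increment beyond volume, age and region, which is smaller if lesion burden and brain volume are correlated. Nor is the gain free, given the missing-data handling it needs.

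The objection does not answer the omission itself. The predictors are collected, are used in other models, and could be added at little cost.

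**Conclusion.** The point holds as a refinement to a confirmatory analysis; it does not invalidate the test. Adding baseline T2 volume and Gd status would take 80% power to about 81% to 86% for an assumed incremental R² of 0.02 to 0.15, with the low end more likely. The Month 6 covariate is a protocol-consistent choice with a small possible bias, about 0 to 0.2 SE under moderate assumptions. Larger distortion (about 0.5 SE, type I error up to 7.5%) needs both a strong volume-change correlation and a large early treatment effect on volume. All of these sizes rest on assumed brain-volume inputs. What the documents do establish is the covariate list, the availability of the baseline values, and the absence of any planned analysis with a different volume covariate.

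**What to change.** Before unblinding, in SAP 3.3.1.2.3:

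1. Add log baseline T2 lesion volume and baseline Gd status (present or absent, with the SAP 3.1 imputation) as covariates. Keep percent change from Month 6 as the response.
2. State a simple treatment-blind rule for missing baseline T2 volume, for example the overall mean, so that nobody is dropped.
3. Fit the model with screening normalized brain volume and its visit interaction in place of the Month 6 terms, at least as a sensitivity analysis, with the same kind of rule for missing values. If it is made the primary model, report the Month 6 version as the sensitivity analysis.
4. Record the change from Protocol 9.4.3. The SAP version history already records a similar step, when baseline EDSS and Gd status were added to the Cox model.

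The cost is SAP wording, two parameters if the new covariates enter as main effects (more with visit interactions), one missing-baseline rule and one extra model fit. No new data are needed.

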- Dose regimen: 60 mg once daily

Investigational medicinal product(s)

• Formulation: placebo to match SAR442168 film coated tablet

VV-CLIN-0579238 21.0

- Route(s) of administration: oral
- Dose regimen: once daily

Noninvestigational medicinal product(s)

- Formulation: MRI contrast-enhancing preparations
- Route(s) of administration: intravenous (IV)
- Dose regimen: per respective label

Property of the Sanofi Group - strictly confidential

Temporary investigational medicinal product (IMP) interruption due to surgery

If surgery is needed during the study, consider the benefit-risk of withholding the IMP for at least 3 to 7 days pre- and post-surgery and the risk of bleeding.

Devices

Not applicable.

Long-term safety study

After the end of this study, participants who complete the trial and are taking the IMP treatment until the end of the trial (double-blind or open-label SAR442168 if meeting 6-month CDP) may be offered the option to participate in a long-term safety (LTS) study for an additional 2 years, or until SAR442168 is approved in their respective country, whichever comes first. Details of the LTS study will be described in a separate protocol.

Duration of study (per participant)

The duration of treatment will vary for individual participants, depending on the time of recruitment. Considering the recruitment period of approximately 24 months and an assumed event rate (discussed below), the duration of the study should be approximately 48 months. All recruited participants will be followed in the study until the common study end, which will be estimated and announced by the Sponsor to ensure that approximately 288 events of 6-month CDP have been observed before the study end.

Statistical considerations:

• Primary endpoint:

The primary estimand will be the treatment difference between SAR442168 and placebo in time to onset of 6 month-CDP regardless of completion of the treatment period. This estimand corresponds to a "treatment policy strategy". This estimand will be considered primary for supporting regulatory decision making.

The time to onset of 6-month CDP will be analyzed by a Cox proportional hazards model with terms for treatment, age at screening (>40, \leq 40 years), geographic region (US, non-US), baseline EDSS score, and baseline Gd-enhancing T1 lesions (0, \geq 1). A log-rank test stratified by age at screening (>40, \leq 40 years) and geographic region (US, non-US) to compare SAR442168 to placebo will also be examined.

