4 STUDY DESIGN

4.1 OVERALL DESIGN

This is a Phase 3, randomized, double-blind, 2-arm, placebo-controlled, parallel-group, multicenter, event-driven (6-month CDP) trial with a variable treatment duration ranging from approximately 24 to 48 months in participants with NRSPMS.

The study will consist of the following study periods:

Screening period: Day -28 to Day -1.

Randomization/start of IMP: Eligible participants will be randomly assigned at a 2:1 ratio to receive oral SAR442168 (60 mg) daily or matching placebo daily.

Intervention period: Double-blind treatment period for assessment of efficacy and safety up to the EOS, as described in Section 4.4.

A month is defined as a period of 28 days by convention.

Safety follow-up period/EOS: 4 weeks after the last dose of study treatment (for participants completing IMP treatment [double blind or open-label, if initiated after 6-month CDP] and not entering the LTS study) to collect safety data.

EOS: A participant is considered to have completed the study if he/she has completed all periods of the study including the EOS Visit, whether remaining on IMP or not.

Participants with 6-month CDP are eligible for open-label active treatment (SAR442168) (Section 6.6.1).

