## 1 INTRODUCTION

#### 1.1 STUDY DESIGN

This is a Phase 3, randomized, double-blind (DB), 2-arm, placebo-controlled, parallel group, multicenter, event-driven (6-month confirmed disability progression [CDP]) trial with a variable treatment duration (minimum of approximately 18 to 24 months) in participants with nonrelapsing secondary progressive multiple sclerosis (NRSPMS).

Approximately 1700 participants will be screened to achieve up to 1290 participants randomly assigned to study intervention.

After a screening period of up to 28 days, participants will be randomly assigned at a 2:1 ratio to receive 60 mg oral tolebrutinib or matching placebo daily. Randomization will be stratified by age at screening (>40 versus  $\leq$ 40 years) and geographic region (US versus non-US).

A month is defined as a period of 28 days by convention. As such, 6 months is defined as 24 weeks, 24 months as 96 weeks, and 48 months as 192 weeks.

Participants who complete the study intervention period (DB or open-label [OL] tolebrutinib if meeting 6-month CDP) may be offered the option to participate in a long-term safety (LTS) study. For participants who complete the study intervention period (DB or OL, if meeting 6-month CDP) and do not enter the LTS study, a final follow-up visit to collect safety data is performed 4 weeks after the last dose of study intervention. A participant is considered to have completed the study if he/she has completed all periods of the study including the end-of-study (EOS) visit, whether remaining on study intervention or not.

Study primary analysis will be conducted after study completion, when approximately 288 events of 6-month CDP have been observed, and final database lock.

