#### 3.3.1.2.2 Number of new and/or enlarging T2 lesions

Number of new and/or enlarging T2 hyperintense lesions over the study period will be analyzed using a negative binomial regression model with robust variance estimation in the ITT population. The robust variance can be estimated by specifying the participant identifier in the repeated statement using SAS PROC GENMOD (version 9.4 or later). The model will include the total lesion count across all magnetic resonance imaging (MRI) scans at all scheduled post-randomization visits during the study period as the response variable, with treatment group, age at screening (>40,  $\leq$ 40 years), geographic region (US, non-US), baseline EDSS score, and baseline number of T2 lesions as covariates. Log transformed observation duration from screening MRI to last available MRI scan will be the offset variable. The estimated mean number of lesions per year for each treatment group and the corresponding two-sided 95% CI will be estimated from the negative binomial model where the adjusted mean value within treatment group is based on a sample size dependent weight within each categorical covariate (ie, weight by overall proportion of participants in each stratum or categorical factor, also called "population weight"). The relative reduction on tolebrutinib compared to placebo, its 95% CI, and p-value will be provided. No imputation for missing data due to early study withdrawal will be performed.

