## 4 SAMPLE SIZE DETERMINATION

Approximately 1700 participants will be screened to achieve up to 1290 randomly assigned to study intervention (2:1 randomization ratio of tolebrutinib to placebo). This study is planned as an event-driven trial based on 6-month CDP. The study will continue until approximately 288 events are projected to have occurred to provide 80% power to detect a 30% risk reduction in 6-month CDP with tolebrutinib compared to placebo (2-sided  $\alpha = 0.05$ ). The following assumptions were used for the calculations: 2-year placebo event rate of 23.6%; annual discontinuation rate of 10%; constant hazard rates using a log-rank test; estimated enrollment period of 24 months with the last randomized participant followed for 24 months.

Actual recruitment and disability event rates may vary; therefore, it is possible to stop with a reduced sample size of around 1100 and still maintain study power by extending the duration of the trial, if needed, to reach approximately the same number of events. For example, it could be that the last randomized participant is followed for around 30 months instead of 24, if necessary. Additional recruitment of participants will not substantially reduce the trial duration. In any case, the power is based on the number of events, and the actual trial duration will be dependent on the observed placebo rate and treatment effect.

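### The brain-volume contrast at EOS takes no account of time to EOS, which ranges from about 18 to 42 months after Month 6: a modest, avoidable loss of precision, not bias

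*SAP*

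**What the plan says.** The protocol (4.1) plans a "variable treatment duration ranging from approximately 24 to 48 months in participants with NRSPMS". The synopsis adds that "All recruited participants will be followed in the study until the common study end", so a participant's time to EOS depends on the randomization date. SAP section 4 assumes an "estimated enrollment period of 24 months with the last randomized participant followed for 24 months". It also allows for a smaller trial in which "it could be that the last randomized participant is followed for around 30 months instead of 24, if necessary".

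SAP 3.3.1.2.3 models percent change in brain volume from Month 6. The terms are treatment, the two stratification factors, visit, treatment by visit, Month 6 volume and Month 6 volume by visit. On the test it says "Comparisons between treatment arms will be made using least squares means (LSM) contrasts at the EOS". Table 7 in SAP 5.4 gives EOS its own nominal visit, closing on the EOS date whatever the elapsed time. An analogous model covers "Change from baseline in SDMT number of correct substitutions, CVLT-II total correct and MSQoL-54 physical and mental health composite scores at the EOS".

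The lesion-count model in SAP 3.3.1.2.2 does handle follow-up time: "Log transformed observation duration from screening MRI to last available MRI scan will be the offset variable". Brain volume is the last step of the hierarchy in SAP 3.5; SDMT, CVLT-II and MSQoL-54 are not in it. Apart from rank ANCOVA and, for brain volume, exclusion of data after open-label start, no sensitivity analysis of the continuous secondary endpoints is planned.

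**The concern.** Brain volume falls with time, so a participant scanned 42 months after Month 6 is expected to have lost more than one scanned at 18 months. The MMRM places both values at one visit level with one mean per arm. The predictable part of that difference then counts as residual variance in the contrast tested under alpha control. For participants who withdraw, the implied EOS mean is the one for average follow-up, not for the time at which each would have reached EOS.

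Planned time to EOS is fixed by the randomization date and the common end date. Treatment cannot affect it, so adjusting for it carries none of the risk of adjusting for a post-randomization variable. What is at stake is some precision on the last step of the hierarchy.

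**Working it through.** **The plan's own figures.** Accrual of 24 months plus 24 months' minimum follow-up gives 24 to 48 months from randomization, as the protocol states. With uniform accrual the mean is 36 months, the top of the protocol's expected 33 to 36. The only power figure in the documents concerns the primary endpoint: √(288 × 2/3 × 1/3) × |ln 0.70| − 1.96 = 8 × 0.357 − 1.96 = 0.89, or 81.4% power against the stated 80%. It tells us nothing about brain volume.

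**Spread of elapsed time.** From Month 6 the range is 18 to 42 months (ratio 2.33), with mean 30 and SD 24/√12 = 6.93. Months are 28 days, so in years the mean is 30 × 28/365.25 = 2.30 and the SD is 0.531. The mean square is 2.30² + 0.531² = 5.57.

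**Added variance at EOS.** Let L be annual loss, s the slope SD and e the error SD. All three are assumptions. With a linear mean trend,

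ratio (no time term / with time term) = 1 + (0.531 L)² / (5.57 s² + e²).

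The share of variance removed is 1 − 1/ratio, and the excess SE is √ratio − 1.

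| L (%/yr) | s | e | ratio | variance removed | excess SE |
|---|---|---|---|---|---|
| 0.3 | 0.5 | 0.3 | 1 + 0.0254/1.483 = 1.017 | 1.7% | 0.9% |
| 0.3 | 0.4 | 0.3 | 1 + 0.0254/0.981 = 1.026 | 2.5% | 1.3% |
| 0.5 | 0.5 | 0.3 | 1 + 0.0705/1.483 = 1.048 | 4.5% | 2.4% |
| 0.5 | 0.4 | 0.3 | 1 + 0.0705/0.981 = 1.072 | 6.7% | 3.5% |
| 0.7 | 0.3 | 0.4 | 1 + 0.138/0.661 = 1.209 | 17.3% | 10.0% |

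The last row is the fast, homogeneous case; with e = 0.3 it reaches 19%.

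Under the 30-month option the range from Month 6 is 24 to 48 months. The mean is 36 months (2.76 years) and the mean square 2.76² + 0.531² = 7.90. Then L = 0.3, s = 0.5, e = 0.3 gives 1 + 0.0254/2.065 = 1.012, a 1.2% cut. L = 0.5, s = 0.4 gives 1 + 0.0705/1.354 = 1.052, a 5.0% cut.

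**Check with a repeated-measures model.** The formula uses EOS values only. A simulation with unstructured covariance (1100 participants, 2:1, 10% dropout per year, assumed slopes and SDs) gave variance ratios of 1.02 to 1.06 at moderate inputs and 1.20 at the extreme, with no material shift in the estimate.

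**Power and type I error.** A second simulation used completers' EOS values, 1290 participants and an assumed effect of 0.2 SD. Let R be the mean change at the mean EOS time divided by the SD at a fixed time.
- At R = 1 the SE without the time term was 1.9% larger. Power was 79 to 80% without the term and 81 to 82% with it.
- Across R = 0.25 to 1.5 the gain was about 0 to 3 points.
- Type I error was 4.8% without the term and 5.1% with it.

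**SDMT, CVLT-II, MSQoL-54.** Measured from randomization, the coefficient of variation of time is 6.93/36 = 0.192, so the added variance is 0.037 R²: 0.2% at R = 0.25, 0.9% at 0.5 and 3.7% at 1.

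**The case against.** The strongest reply is that nothing here is an error. The endpoint is defined as change at EOS and the SAP analyses that endpoint. Randomization balances time to EOS, and the unadjusted test keeps its size. By-visit LSM plots and summaries already show differences at fixed times. All of this stands, and it limits the point to precision.

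Four stronger readings are tempting, and the documents do not support them.
- **Bias or an invalid test.** A reader might infer this from the twofold spread. It does not follow, because the spread is the same in both arms by randomization.
- **An internal inconsistency with the lesion model.** That endpoint is a rate per year and needs an exposure offset; a change score at a visit does not. The comparison shows only that the SAP recognizes variable follow-up elsewhere.
- **Four alpha-controlled tests affected.** Only brain volume is in the hierarchy. For the other three endpoints the gain is close to nil if mean change is small.
- **A saving in participants.** The variance percentages should not be converted into a head count on the full sample. The inputs are assumed. If the planned 10% annual discontinuation means loss of the EOS value, only about 73% would contribute one.

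A further objection concerns the remedy. A time-by-visit interaction at every visit would distort the LSMs at Months 42 and 48, which only early enrollees can reach. That is correct, so the term belongs at EOS alone.

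**Conclusion.** The point holds for brain volume as a modest, avoidable loss of precision. Under assumed loss of 0.3 to 0.5% per year and slope SD 0.4 to 0.5, the time term would remove about 1 to 6% of the variance of the EOS contrast (about 0.5 to 3% in SE). The closed form comes just under 7% at the least favourable corner of that range. About 17% or slightly more needs loss near 0.7% per year with slope SD 0.3. These figures rest on uniform accrual, a linear mean trend, and slopes and SDs that the documents do not give.

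The SAP (1.1) describes a "variable treatment duration (minimum of approximately 18 to 24 months"), whereas the protocol gives 24 to 48. The two should be reconciled. With an 18-month minimum and the same 24-month spread, the interval from Month 6 would be 12 to 36 months, a threefold range, and the loss somewhat larger.

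**What to change.** Keep the estimand and the MMRM. In SAP 3.3.1.2.3, add to the brain-volume model centred planned time from Month 6 to the common study end, with a coefficient at the EOS visit level only. Derive it for every randomized participant, including those who withdraw, from the randomization date and the announced common end date. Do not use the date of the last scan, which can depend on what happened after randomization. With no treatment-by-time term, the dates derived for withdrawals affect only the centring and the displayed arm means, not the contrast.

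The same term, with time counted from randomization, may be added to the SDMT, CVLT-II and MSQoL-54 models. If the primary model cannot be changed, specify it as a supplementary analysis of brain volume.

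The cost is one extra parameter per model, one SAP line and a derived planned EOS date for withdrawals. The term does not repair the Toeplitz and AR(1) fallback structures, which treat EOS as equally placed in the visit sequence for everyone. Moving the contrast to a fixed Month 24 visit is not a good alternative: in the second simulation, with an effect growing linearly, power fell to about 42 to 65%.
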